13.4.5. Concomitant Medications and Concomitant Therapies

Concomitant medications will be categorized using a standardized coding dictionary and listed. Concomitant therapies will be listed only.

13.5. Other Statistical Considerations

13.5.1. Significance Levels

The type I error rate will be set at the 5% significance level for the primary efficacy analysis.

All secondary and exploratory efficacy analyses will be performed at the 2-sided 5% significance level.

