4.1. Primary Efficacy Objective

The primary efficacy objective of the study is to investigate the efficacy of SI-613 for the treatment of OA knee pain by showing a greater reduction in pain as measured by the WOMAC visual analog scale (VAS) pain subscore over a 12-week evaluation period in subjects treated with SI-613 compared with subjects treated with placebo. The primary efficacy objective will be tested using the null hypothesis that there is no difference in the mean change from the pretreatment measure of pain relief (WOMAC VAS pain subscore) between SI-613 and placebo over 12 weeks.

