13. STATISTICS

13.1. Power and Sample Size Determination

Approximately 80 subjects with symptomatic primary OA of the knee will be randomized. Forty subjects per group (80 total subjects) were calculated to provide an 80% probability that a 3 mm (or greater) treatment difference point effect for the primary endpoint will be observed, but not necessarily at a statistically significant level. This assumes that the true treatment difference is 7.5 mm and standard deviation is 23 mm based on the previous Japanese 613/1022 study.

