13.4.3. Efficacy Analyses

13.4.3.1. Primary Efficacy Analysis

The primary efficacy analysis will be performed on the WOMAC VAS pain subscore using longitudinal analysis to incorporate information from pain scores assessed at Weeks 1, 2, 4, 6, 8, 10, and 12. A direct likelihood approach as implemented in the SAS MIXED procedure will be used to estimate model parameters designed to reflect group-specific mean values over time. The primary efficacy hypothesis concerns the over a 12-week evaluation period from Week 1 to Week 12, and the group comparison is defined as the average effect over assessments during these weeks. Supporting analyses involve comparisons reflecting group differences at the various study visits, including landmark analysis at Week 12 and early onset of efficacy at Week 1. In all cases, model parameters will be used to determine comparisons for which statistical significance against null zero hypotheses and corresponding 95% confidence intervals will be provided. The basic longitudinal model will be specified as a repeated-measures model that expresses the pain score as a linear function of treatment, time, treatment-by-time interaction, and clinically relevant covariates (pretreatment pain measurement, K-L score, and sex) and a fixed-site effect.

The model is designed to account for correlations among responses over time and to use these correlations to implicitly impute missing values from the non-missing values. The type=UN option in the SAS MIXED procedure will be used to model correlation patterns across time.

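### Does leaving the side of the primary 5% test unstated in section 13.5.1 leave the primary verdict open?

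*Combined protocol and SAP*

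**What the plan says.** Section 13.5.1 (Significance Levels) consists of two sentences. For the primary analysis: "The type I error rate will be set at the 5% significance level for the primary efficacy analysis". For the rest: "All secondary and exploratory efficacy analyses will be performed at the 2-sided 5% significance level".

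Section 4.1 describes the aim directionally, as "showing a greater reduction in pain" on SI-613. It then names the hypothesis to be tested, which is the "null hypothesis that there is no difference in the mean change" between the arms.

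Section 13.4.3.1 defines the primary comparison as the average effect over the Week 1 to Week 12 assessments, with visit-wise comparisons as support. For all of these it says that "statistical significance against null zero hypotheses and corresponding 95% confidence intervals will be provided".

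Section 13.1 gives the basis for the sample size: "Forty subjects per group (80 total subjects) were calculated to provide an 80% probability that a 3 mm (or greater) treatment difference point effect" on the primary endpoint "will be observed, but not necessarily at a statistically significant level". The assumptions are a true difference of 7.5 mm and an SD of 23 mm. Section 13.3 leaves the definition of major protocol deviations to a statistical analysis plan. The supplied document contains no separate text of that plan.

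**The concern.** The authors named a side for every efficacy test except the one that matters most. The second sentence of 13.5.1 is limited to secondary and exploratory analyses, so it cannot be stretched to cover the primary. The contrast could be read as deliberate, and the directional wording of the objective gives that reading some support. Section 13.1 cannot settle the matter, because it quotes no power for a test.

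If the side were truly undecided, the same data could pass or fail the primary test according to a choice made after unblinding. A one-sided 5% test would also double the chance of a false positive in favour of SI-613, from 2.5% to 5%. A success could then be declared beside a 95% interval that includes zero.

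**Working it through.** **Inputs.** 40 per group, true difference 7.5 mm, SD 23 mm and the 3 mm benchmark, all from 13.1; 1:1 allocation from 13.2; 5% level from 13.5.1; 95% interval from 13.4.3.1.

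**The plan's own figure.** SE = 23 × √(2/40) = 5.143 mm. P(observed ≥ 3 mm) = Φ((7.5 − 3)/5.143) = Φ(0.875) = 80.9%. This reproduces the stated 80%. Neither alpha nor the side enters the calculation.

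**What the side would change.** Threshold = z × SE; power = 1 − Φ(z − 7.5/SE), with 7.5/5.143 = 1.458.

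| Reading | z | Observed difference needed | Power at 7.5 mm |
|---|---|---|---|
| One-sided 5% | 1.645 | 8.46 mm | 1 − Φ(0.187) = 42.6% |
| Two-sided 5% | 1.960 | 10.08 mm | 1 − Φ(0.502) = 30.8% |

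The verdicts differ with probability 42.6% − 30.8% = 11.8%. With the t distribution on 78 df, the thresholds are 8.56 and 10.24 mm, the powers 42.1% and 30.2%, and the difference 11.9%.

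**Sensitivity.** Over assumed SDs of 15 to 26 mm the gap runs from 11.0 to 12.5 points. With an assumed 32 evaluable per group it is 11.1. Under normal theory it can never exceed 2Φ((1.960 − 1.645)/2) − 1 = 2Φ(0.1575) − 1 = 12.5%. The 12% is thus a general property of comparing these two tests at moderate power and says little about this trial in particular.

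**Which reading fits the text.** Take an observed difference of 9 mm, inside the band.

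- z = 9/5.143 = 1.75, so p = 0.040 one-sided and 0.080 two-sided.
- 95% interval: 9 ± 10.08, or −1.1 to 19.1 mm. It includes zero and agrees with the two-sided p-value.
- 90% interval: 9 ± 8.46, or 0.5 to 17.5 mm. It excludes zero and is the interval that agrees with the one-sided p-value.

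Section 13.4.3.1 pairs the test with the 95% interval, not the 90%. Only the two-sided 5% reading makes that pairing coherent, and it is also the natural test of the no-difference null in 4.1.

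**The case for a change.** The best argument for a change is that the fit with other sections is inference. No sentence in the supplied text calls the primary test two-sided, the neighbouring sentence shows that the authors knew how to say so, and one word would close the gap. All of that is true. Since 4.1 says the objective will be tested, a primary verdict will be issued even though the trial was not sized for significance. But the omission would matter only if a careful analyst could go either way. The sole support for one-sided is the directional objective, which is ordinary wording for a superiority trial and is followed at once by the no-difference null. A separate analysis plan might also state the side; that cannot be checked here, and the conclusion does not rely on it.

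It can also be argued that the effective SD of an adjusted seven-visit average may be below 23 mm. For an SD between 7.5/(1.960 × √0.05) = 17.1 and 7.5/(1.645 × √0.05) = 20.4 mm, an observed difference equal to the assumed 7.5 mm would fall in the disputed band. The arithmetic is right, but the documents give no SD below 23 mm. The plan's 80% fits 23 mm (80.9%) better than 20 mm, where Φ(4.5/4.472) is about 84%. At 23 mm an observed 7.5 mm is non-significant on both readings.

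A further suggestion is to add power figures to 13.1, with a statement that 3 mm is not a success criterion. This does not follow from the missing side. Section 13.1 already says that the 3 mm difference need not be statistically significant, and nowhere makes it a criterion for success.

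**Conclusion.** No change to the plan follows. The missing side in 13.5.1 is a gap in wording that an analyst fills correctly from 4.1 and 13.4.3.1, by testing at two-sided 5% and reporting the 95% interval. The estimate, interval, model and sample size are the same whether or not the word is there.

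On the protocol's inputs, and treating the primary endpoint as a simple two-group comparison as 13.1 does, the one-sided reading would alter the verdict only for observed differences of about 8.5 to 10.1 mm, with a probability of about 12% at a true 7.5 mm. Even then the reported 95% interval would include zero, so a reader would see that a one-sided claim did not match the planned inference. The conclusion rests on reading the interval statement in 13.4.3.1 as covering the primary comparison, which its wording does.

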13.5.2. Missing Data

For the efficacy analysis based on repeated-measures models of continuous endpoints, missing data will be implicitly handled via a mixed-effect model, without explicit imputation. Inferences based on this approach are unbiased under the assumption of missing at random, which is a weaker and more generally true assumption than missing completely at random. Sensitivity analysis based on multiple imputation methods which changes imputation methods by missing pattern such as discontinuations due to AEs, lack of efficacy, and other will be performed for the ITT population.

For the efficacy analysis based on percentages of positive responders, subjects who discontinue the study because of target knee AEs or lack of efficacy and subsequently have missing efficacy data will be classified as nonresponders.

No replacement of any missing data will be made for the safety analyses.

13.5.3. Visit Windows

All data collected during study follow-up will be displayed and analyzed according to the actual visit data in the eCRF. Assessments taken outside of windows described in the protocol will be displayed according to the eCRF assessment recorded by the investigator.

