6.3. Subject Withdrawal Criteria

Subjects will be encouraged to adhere to the protocol and complete all required assessments. A subject will be discontinued from the study for any of the following medical or administrative reasons:

- A treatment-emergent AE or considerable worsening of an AE that, in the judgment of the investigator or medical monitor, represents an unacceptable risk to the subject and warrants stopping the subject's participation in the investigational study. The investigator must follow the subject until the AE resolves or satisfactorily stabilizes.
- Pregnancy.
- Death of subject.
- Poor response of a subject to the investigational product such that the investigator determines that the subject needs treatment that excludes them from the protocol.
- A critical deviation from the inclusion or exclusion criteria that leads the investigator or medical monitor to determine that continued injections of SI-613 or placebo are not appropriate for ethical or safety reasons.
- Having joint replacement of the target knee
- Receiving an IA injection into the target knee joint (e.g., HA, corticosteroids, or chondroprotective agents) during the study.
- Participation in another clinical study.
- Development of human immunodeficiency virus infection (as assessed by a positive test for human immunodeficiency virus) or active hepatitis.

- Development or diagnosis of alcohol or other substance abuse.
- If the investigator judges it impossible to continue the study for a subject because
 - o The subject does not comply with protocol requirements
 - o The subject is lost to follow up
 - o There are technical issues at the site
- Investigator discretion at any time.
- Subject's request.
- Sponsor's discontinuation of the study at a site.
- Premature termination of the study by the sponsor.

Any enrolled subjects desiring to discontinue prior to study completion should be encouraged to continue in the study and adhere to the protocol and subsequent regularly scheduled safety and efficacy evaluations. Subjects who are discontinued outside of any scheduled visit will be encouraged to complete the early termination visit at the time of withdrawal. Subjects who are discontinued during a scheduled visit will be encouraged to complete all assessments for both that study visit and the early termination visit at the time of withdrawal. A subject who withdraws following the injection will not be replaced.

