7.2.7. Early Termination Visit

If a subject must withdraw early from the study, all procedures normally included in the last visit of the study (i.e., Visit 11) will be performed. In addition, the reason(s) for withdrawal from the study will be collected.

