7.2.8. Unscheduled Visits

There may be situations in which the investigator decides to have a subject return for an unscheduled visit after the subject contacts them about an AE or other health information. Therefore, additional examinations may be conducted as necessary to ensure the safety and well-being of subjects during the study. Electronic case report forms (eCRFs) should be completed for each unscheduled visit. The AE and all required information should be recorded on the appropriate eCRF, and the subject's record should include all relevant information.

Table 2: Study Schedule

	Screening	Randon	mization	Follow-up										
77'	Baseline 2			3	3 4 5 6				7 8 9					11
Visit	1	-							,		Ů		10	26/ Early
Week	-2 to -1		0		2		4	6	8		10	12	18	Termination
Day	Day -14 to		ay	Day	Day		Day Da			ay	Day	Day	Day	Day
	-7		I	8	15		29	43		5 7	71	85	127	183
Window (days)				± 2	± 2		7	± 6		7	± 6	± 7	± 14	± 14
		Before Injection	Injection			Before Injection	Injection		Before Injection	Injection				
Informed Consent*	X	,					-			,				
Confirm Rescue Acetaminophen Washout ¹	X	X		X	X	X		X	X		X	X	X	X
Wash Out Prohibited Medications/Therapies ²	X													
Concomitant Medications and Therapies ³	X	X		X	X	X		X	X		X	X	X	X
Prior Medications	X													
Medical History	X	X												
Vital signs ⁴	X	X		X	X	X		X	X		X	X	X	X
BMI (Height, Weight)	X													
X-ray ⁵	X													
Assess K-L Score	X													
Assess femoral-tibial angle	X													
Urine Drug Screen	X													
Laboratory Tests ⁶	X					X			X			X		X
Pregnancy Test ⁷	X	X				X			X					X
Acetaminophen Consumption Assessment		X		X	X	X		X	X		X	X	X	X
Subject Daily Diary Collection and Compliance Assessment		X		X	X	X		X	X		X	X	X	X
Adverse Events ⁸	X	2	X	X	X		X	X	X		X	X	X	X
Target Knee Examination	X	X		X	X	X		X	X		X	X	X	X
Assess Patellar Grinding via Clarke's test	X													
WOMAC Osteoarthritis	X	X		X	X	X		X	X		X	X	X	X

	Screening	Rando	mization	Follow-up											
		Baseline													
Visit	1		2	3	4		5	6		7	8	9	10	11	
Week	-2 to -1		0		2		4	6	8		10	12	18	26/ Early Termination	
Day	Day -14 to -7	Ι	Day I		Day Day Day 8 15 29		Day 43	Day 57		Day 71	Day 85	Day 127	Day 183		
Index ⁹	,				- 10	-		.5			, ,	00	12,	100	
PGIC				X	X	X		X	X		X	X	X	X	
SF-36		X				X			X			X		X	
PASE		X		X	X	X		X	X		X	X	X	X	
CGIC				X	X	X		X	X		X	X	X	X	
50-foot Walk Test ⁹	X	X													
Inclusion/Exclusion Criteria	X	X													
MRI	X^{10}											X^{11}		X ¹¹	
Randomization		X													

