12.2. Synovial Assessment by MRI

T2 fat-saturated image in the sagittal and axial views by MRI for the target knee will be taken at Visit 1, Visit 9, and Visit 11 (or early termination). The independent central imaging evaluator will conduct the synovial assessment of each subject based on the following imaging criteria:

- Hoffa's synovitis score and the synovitis-effusion score according to the semi-quantitative scoring methods of the MOAKS (MRI Osteoarthritis Knee Score)⁹
- Qualitative assessment for the knee joint synovial thickening

The detailed method for MRI assessments will be defined in the separate independent review manual.

Significant aggravations in the synovial assessments for Visit 9 and/or Visit 11 compared to Visit 1 detected by the independent central imaging evaluator will be reported as an AE.

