12.4. Laboratory Tests

Blood will be collected from each subject at Visit 1 (Screening), Visit 5 (Day 29/Week 4), Visit 7 (Day 57/Week8), Visit 9 (Day 85/Week 12), and Visit 11 (Day 183/Week 26 or early termination) to perform a complete blood count (CBC) and complete metabolic profile. Urine will be collected from each subject at Visit 1 (Screening), Visit 5 (Day 29/Week 4), Visit 7 (Day 57/Week8), Visit 9 (Day 85/Week 12), and Visit 11 (Day 183/Week 26 or early termination) for qualitative urinalysis regarding glucose, protein and urobilinogen.

Any abnormal results for these tests will be noted, and changes in the test results that, in the investigator's opinion, are associated with or considered an untoward or unfavorable medical occurrence should be reported as an AE.

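### Does the missing rule for placing an early-termination WOMAC score damage the primary analysis?

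*Combined protocol and SAP*

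**What the plan says.** Section 13.4.3.1 fits a repeated-measures model to pain scores from Weeks 1, 2, 4, 6, 8, 10 and 12. Section 13.5.3 ties each record to its visit: "All data collected during study follow-up will be displayed and analyzed according to the actual visit data in the eCRF". It adds that out-of-window assessments keep the investigator's eCRF label, and it does not mention early termination.

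On withdrawal, Section 6.3 says: "Subjects who are discontinued outside of any scheduled visit will be encouraged to complete the early termination visit at the time of withdrawal". When withdrawal happens during a scheduled visit, the subject is encouraged to "complete all assessments for both that study visit and the early termination visit at the time of withdrawal". Under Section 7.2.7, at early termination "all procedures normally included in the last visit of the study (i.e., Visit 11) will be performed", and Section 7.2.6 shows that these include the WOMAC. Table 2 has no separate column for early termination; the visit shares the one labelled "26/ Early Termination". Sections 12.2 and 12.4 make the same pairing.

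Section 13.5.2 relies on the mixed model under missing at random. It plans a multiple-imputation sensitivity analysis that varies with the reason for discontinuation. Section 13.4.3.2 repeats the efficacy analyses over Weeks 1 to 26. Section 13.3 defers some details to a statistical analysis plan whose text is not part of the supplied document.

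**The concern.** Take a subject who withdraws on Day 40, between Visits 5 and 6, and attends an early-termination visit. The WOMAC is collected, but its eCRF visit is not one of the seven in the primary model. Read literally, the score is never used. In the Weeks 1 to 26 repeat it might even be taken as a Week 26 value.

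This matters because the protocol expects withdrawal for pain: Section 6.3 lists poor response and Section 13.5.2 names lack of efficacy. Missing at random is easier to defend when the last pain score before withdrawal is in the model. The trial is also sized on the observed difference reaching 3 mm, not on significance, so a shift in the estimate bears directly on the design goal.

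**Working it through.** **1. The plan's own figure.** Section 13.1 gives 40 per arm, a true difference of 7.5 mm and an SD of 23 mm.

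SE = 23 × √(2/40) = 5.143 mm. P(observed difference ≥ 3 mm) = Φ((7.5 − 3)/5.143) = Φ(0.875) = 0.809, which agrees with the stated 80%.

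**2. Which days are affected.** The Table 2 windows are Days 6–10, 13–17, 22–36, 37–49, 50–64, 65–77 and 78–92. They run unbroken from Day 22 to Day 92; after the first injection only Days 2–5, 11–12 and 18–21 lie outside every window. A withdrawal at a scheduled visit is largely covered by Section 6.3.

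**3. Size if the score is left out.** All withdrawal inputs are assumptions:
- withdrawal before Week 12 of 14%/8%, 26%/16% (placebo/active) or 20%/20%;
- a link between withdrawal and current pain of 0, 0.5 or 1.5 log-odds per SD;
- half or all withdrawals between visits;
- 60% or 100% of early-termination visits attended.

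Unused scores per trial, with unequal withdrawal, run from 40 × (0.14 + 0.08) × 0.5 × 0.6 = 2.6 to 40 × (0.26 + 0.16) = 16.8. A large-sample simulation (70,000 per arm, two seeds, unstructured covariance) gave this bias in mm; negative means toward zero:

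| Link | 14%/8%, all between visits | 26%/16%, all | 14%/8%, half | 26%/16%, half |
|---|---|---|---|---|
| 0 | +0.01 | +0.01 | +0.01 | +0.01 |
| 0.5 | −0.07 | −0.12 | −0.04 | −0.06 |
| 1.5 | −0.25 | −0.48 | −0.13 | −0.25 |

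With equal withdrawal the bias is 0.03 mm or less. Monte Carlo standard errors of differences are 0.004 to 0.062 mm, so the smallest entries may not differ from zero. The worst entry is 0.48/5.143 = 9% of the SE. The chance of observing 3 mm becomes Φ((7.5 − 0.12 − 3)/5.143) = 0.803 at the worst moderate entry and Φ((7.5 − 0.48 − 3)/5.143) = 0.783 at the worst strong one.

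**4. A second, harsher set.** This used 1,500 trials of 40 per arm, nominal withdrawal of 10%, 20% or 30%, two correlation patterns, every withdrawal between visits and every score obtained. The first column is the bias when the score is left out; the second is the bias when it is placed at the next scheduled visit.

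| Withdrawal | Left out | Next visit |
|---|---|---|
| Unrelated to pain | 0.06 mm or less | 0.10 mm or less |
| Pain-driven in both arms | 0.07–0.46 mm toward zero | 0.05–0.21 mm favouring SI-613 |
| Pain-driven in placebo only | 0.20–1.50 mm toward zero | 0.13–0.81 mm favouring SI-613 |

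The 1.50 mm case (30% withdrawal) is 1.50/5.143 = 29% of the SE and lowers the chance of observing 3 mm to Φ((7.5 − 1.5 − 3)/5.143) = 0.720.

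**5. What a finer rule would buy.** Suppose the score goes to the nearest unfilled scheduled week within 7 days. In the setting of step 3, with all withdrawals between visits and all early-termination visits attended, the bias at links 0/0.5/1.5 becomes +0.03/+0.03/+0.04 mm (14%/8%) and +0.05/+0.06/+0.08 mm (26%/16%). With no link this is slightly worse than leaving the score out. About 4 in 10 scores (3.4 of 8.8, or 6.4 of 16.8) still go unmodelled. With visits on nominal days, the rule would model scores from 47 days, of which 6 − 4 = 2 (Week 1), 2 (Week 2), 7, 6, 7, 6 and 7 = 37 already lie in the next visit's own window. The other ten include Days 2–5, counted as Week 1, and Days 9–12, counted as Week 2, against the protocol's ±2 days at both visits.

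**6. If the score were filed as Week 26.** In the simulation of step 3, with unequal withdrawal, the Week 26 difference rises by 0.15–0.44, 0.45–1.15 or 0.91–2.06 mm at links 0, 0.5 and 1.5. With equal withdrawal it rises by 0.06 mm or less. The Weeks 1 to 26 average moves by 0.20 mm or less.

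**The case for a change.** The best case for a change is that the score is already collected, a rule costs a few sentences, and the same model serves most secondary endpoints. With no rule, an analyst could omit the score, move it to the next visit or call it Week 26. The planned imputation analysis does not say that it uses the score. In the one-sided scenarios of step 4 the loss is no longer trivial.

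Part of this stands. No supplied section places the score, and the choice belongs before unblinding. Three things weaken the rest.

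- Omission is only one reading. Section 13.5.3's wording on actual visit data could mean the visit date, and a mapping convention would normally sit in the analysis plan that Section 13.3 mentions.
- Not every early-termination score is a clean reading. Section 6.3 lists target-knee injection and joint replacement as discontinuation reasons, so the score may follow them. An unplanned visit also cannot guarantee the two-day acetaminophen abstention of Section 9.2. The simulations treat every score as clean.
- Some scores will never exist. The visit is only encouraged, and Section 6.3 also lists "The subject is lost to follow up" as a reason. At 60% attendance the 7-day rule leaves a bias of −0.01 to −0.14 mm at links 0.5 and 1.5.

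Responder endpoints are largely protected by the nonresponder rule in Sections 13.4.3.2 and 13.5.2.

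**Conclusion.** No change follows. This is a missing operational detail that analysts fill sensibly when they write the visit-mapping specification. Under withdrawal that is unrelated to pain or equal between arms, leaving the score out costs essentially nothing. Where pain drives withdrawal in both arms, the cost is 0.04 to 0.48 mm across the two sets of runs, at most about 9% of the 5.14 mm SE. It exceeds that only when withdrawal is pain-driven in placebo alone, reaching 1.50 mm at 30%. All of these rates and links are assumed.

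The material shifts run against SI-613, so a favourable primary result is not put in doubt. The placement rules tried exchange that conservative error for a smaller one that, when all scores are obtained, favours SI-613. The Week 26 reading is not stated in the plan, and it barely moves the Weeks 1 to 26 average. The imputation by discontinuation reason in Section 13.5.2 already addresses the same departure from missing at random.
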